## 1 Introduction

### 1.1 Purpose

This Statistical Analysis Plan (SAP) describes primary and secondary outcome measures of the Tatelo study that will be included in the primary manuscript(s), and which address, at a minimum, the primary objective of the study for Steps 1, 2 and 3 (see study design section below for description of the Steps). This SAP outlines the general statistical approaches that will be used in the analysis of these Steps of the study. It has been developed to facilitate discussion of the statistical analysis components among the study team, and to provide agreement between the study team and statisticians regarding the statistical analyses to be performed and presented in the primary analysis report. It also describes the results for the primary and secondary outcome measures that will be posted on ClinicalTrials.gov.

Detailed outlines of tables, figures, and coding descriptions for the Analysis Report will be included in the Analysis Implementation Plan (AIP).

Analyses will be finalized once the last participant has completed the Week 24 study visit of Step 3 and any relevant queries have been resolved. Analyses addressing the pharmacokinetic (PK) component of the primary objective of the study using PK data collected in the PK Step and in Step 1a have been undertaken previously based on a PK Step SAP.

### 1.2 Version History

Version 2.0 of the SAP includes the following changes compared with the previous version:

- Clarified primary safety outcome as including adverse events occurring through 30 days after the last study visit (this aligns with the intended outcome measure as posted on clinicaltrials.gov).

- Revised plans for exploratory analysis evaluating characteristics of participants who experienced virologic rebound during Step 2 versus participants who did not experience rebound.
- Minor edits for clarification.

[figure not shown]
## 2 Study Overview

### 2.1 Study Design

This study is a phase I/II, multi-site clinical trial of dual treatment with two broadly neutralizing monoclonal antibodies (bNAbs), VRC01LS and 10-1074, offered to HIV-1 infected virally suppressed children. The study planned to enroll up to 40 children from two participating sites in Botswana (Gaborone and Francistown). Participants eligible for Tatelo were children with HIV who were enrolled in the Early Infant Treatment (EIT) Study (and started antiretroviral treatment [ART] shortly after birth), were at least 96 weeks old, received ART for at least 96 weeks, had HIV RNA <40 copies/mL for at least 24 weeks prior to entry, were willing to receive infusions of bNAbs, and met all other entry criteria.

There are 4 Steps in the protocol: PK Step, Step 1, Step 2, and Step 3. In the PK Step, ART was continued and 6 study participants underwent safety evaluations and PK testing following a single dose of VRC01LS (administered at Week 0, Week 4, and Week 8), and 6 study participants underwent safety evaluations and PK testing following a single dose of 10-1074 (administered at Week 0, Week 4, and Week 8).

Additional participants were eligible to be enrolled in Step 1 and were followed through Steps 1, 2 and 3. In Step 1, ART was continued and dual bNAb treatment was given. In Step 2, ART was withdrawn and dual bNAb maintenance treatment continued. In Step 3, dual bNAbs were discontinued and participants re-started ART. Figure 1 provides a schematic of the study. Note that the first six participants enrolled in Step 1 participated in an additional PK component of the study to confirm dual bNAb dosing. This is referred to as Step 1a; PK data from this step have been analyzed previously. All participants were monitored for both safety and viral rebound throughout the study.

**Figure 1: Study Schematic**

## 2.2 Study Objective Addressed in this SAP

This SAP addresses the following primary objective listed in the study protocol for Specific Aim 1 (other than the PK component of the objective for the PK Step and Step 1a which has been addressed previously), which includes the major outcomes for evaluating the effect of the study treatment. Other study objectives in the protocol will be addressed separately.

Analysis of the study objectives below will be analyzed under a proof-of-concept framework. This study does not have a control arm; however, 95% confidence intervals will be reported.

### 2.2.1 Primary Objective

#### 2.2.1.1 Specific Aim 1

To conduct an interventional clinical trial to determine the safety, pharmacokinetics, dosing and antiviral efficacy of up to 24 weeks of maintenance VRC01LS and 10-1074 immunotherapy in early-treated HIV-1 infected children in Botswana.

### 2.3 Hypotheses

#### 2.3.1 Specific Aim 1

VRC01LS and 10-1074 will not be associated with serious adverse events (SAEs), and median trough concentrations at the doses used will be above established target values of 200 mcg/mL and 7.5 mcg/mL respectively [note, Letter of Amendment (LOA) #2 revised PK trough target for VRC01LS to 160mcg/mL at Day 56 of Step 1]. At least 70% of early-treated low-reservoir children will remain with HIV-1 RNA <400 copies/mL after 24 weeks of receiving VRC01LS and 10-1074 maintenance.

## **2.4 Overview of Sample Size Considerations**

Sample size considerations and estimated precision given in version 2.0 of the protocol are in relation to follow-up through the end of Step 2 of at least 20 children. With a sample size of 20 children (the minimum number expected), safety and PK evaluations will be descriptive, and there will be reasonable precision to estimate the proportion with HIV viral suppression.

## **2.5 Overview of Formal Interim Monitoring**

An independent and external Safety Monitoring Committee (SMC) was established to review interim study data, including safety, PK and viral load. These reviews occurred at the end of the PK step, after the first 6 participants have completed at least 8 weeks of follow-up under Step 1 and then at least every 6 months, and as recommended by the SMC. Details are provided in section 13 of version 2.0 of the protocol and in LOA #3.

# **3 Outcome Measures**

## **3.1 Specific Aim 1 Primary Outcome Measures**

- AEs graded for severity according to Division of AIDS Table for Grading the Severity of Adult and Pediatric Adverse Events (DAIDS AE Grading Table), assessed for association with treatment, and measured through 30 days after last study visit. Clinical Research Site staff make an initial assessment of association with treatment, followed by team review. In the event of any discordance, team assessment will be used.
- HIV-1 RNA in plasma through week 24 of Step 2.

## **3.2 Specific Aim 1 Secondary Outcome Measures**

- VRC01LS and 10-1074 concentrations in serum measured through week 32 following Step 1 entry
- Growth characteristics (sex-specific WHO standardized Z-scores for height for age and weight for age) measured at least monthly, including growth trajectories.

# **4 Statistical Principles**

## **4.1 General Considerations**

### **4.1.1 Defining baseline**

Baseline is the date of initiating dual bNAbs in Step 1 (labeled as Day 0 of Step 1).

### **4.1.2 Analysis populations**

The main analysis population is the population of children that receive any infusions in Step 1. Any children that enroll to the study but do not receive any infusions in Step 1 will be included in screening, accrual and eligibility summaries only.

#### 4.1.3 Visit windows and schedule

The baseline visit, as defined above, is considered day 0. Baseline measurements are the last available measurement for a given parameter obtained prior to administration of this first infusion. The visit schedule is based on this day 0.

Per protocol, the scheduled visit window begins at the midpoint from the previous visit and extends to the midpoint with the next visit. During participation in Step 1 or Step 2, if a child needed to discontinue study treatment for any reason, he/she would complete final visit evaluations for the Step and enroll to Step 3.

Children enrolled to **Step 1a** (first 6 participants) had initial visits at Day 0, Day 1, Week 1, Week 4, Week 4 + 1 day, Week 5 and Week 8. Infusions occurred at Day 0, Week 4 and Week 8. Single PK draws were made at all non-infusion visits and at Week 8, while more intensive PK draws occurred on Day 0 (pre-infusion, end of infusion and 1 hour post-infusion) and Week 4 (pre-infusion, end of infusion and 1 hour post infusion at Week 4). The Step 1a follow-up extended beyond Week 8 at 2 week intervals until Week 32 (which also served as Step 2 Week 0), with infusion and single PK draws every 4 weeks. SMC review and approval of Step 1a results was required prior to starting Step 2

**Step 1b** (for participants enrolled after the first six participants in Step 1/SMC review) visits were scheduled at Day 0, Week 1, Week 4, Week 5 and Week 8 (Step 2 Week 0). Dual bNAbs were administered at Day 0, Week 4 and Week 8; PK measures were limited to pre-dose trough at Week 4 and Week 8 (which also served as Step 2 Week 0).

If a participant had a confirmed viral load result  $\geq 40$  copies/mL during Step 1 (either 1a or 1b), he/she would discontinue bNAbs, complete visit procedures equivalent to those outlined for Step 1 Week 8, and enter Step 3 (and not participate in Step 2).

**Step 2** visits occurred every week for the first 4 weeks, then every 2 weeks through Step 2, Week 24, with dual bNAbs administered and PK trough draws every 4 weeks.

If a participant experienced a single viral rebound  $\geq 400$  copies/mL in Step 2, ART was re-started (and bNAbs discontinued). If HIV-1 RNA was  $\geq 400$  copies/mL prior to the end of Step 2, all evaluations ordinarily scheduled at Week 24 were performed immediately prior to ART re-initiation. If HIV-1 RNA was  $\geq 40$  copies/mL but  $< 400$  copies/mL, or if qualitative DNA turned from negative to positive, virologic monitoring tests were repeated weekly. All participants who did not experience viral rebound prior to week 24 entered Step 3 at the same visit as Step 2 Week 24.

In **Step 3** visits were scheduled at 4 weeks from Step 3, Day 0 (which was the same visit as Step 2 Week 24), 12 weeks, and 24 weeks. Participants who entered Step 3 due to viral rebound prior to Week 24 of Step 2 were followed for virologic monitoring visits weekly in Step 3 until HIV-1 RNA returned to  $< 40$  copies. There were no bNAbs administered or PK draws done in Step 3.

#### **4.1.4 Adjustment for multiple comparisons**

The analyses for the Steps 1-3 are descriptive and exploratory and no adjustment for multiple comparisons (e.g. across outcome measures) will be undertaken.

#### **4.1.5 Summarizing continuous variables**

Continuous variables will be summarized using minimum, lower quartile (Q1), median, upper quartile (Q3) and maximum, along with mean and standard deviation.

#### **4.1.6 Missing data**

Participants in this study have been successfully followed with demonstrated high adherence to study evaluations for at least 96 weeks before entering this study, so missing data are expected to be minimal. Missing data will be documented and the potential impact of missing data on the interpretation of results will be considered along with taking into account the specific reasons for missingness.

#### **4.1.7 Defining SAEs**

For this study a SAE, as defined by the International Conference on Harmonisation (ICH), is an AE following an infusion of a bNAb that:

- Results in death
- Is life-threatening
- Requires hospitalization or prolongation of existing hospitalization
- Results in persistent or significant disability/incapacity
- Is a congenital anomaly/birth defect or
- Is an important medical event that may not be immediately life-threatening or result in death or hospitalization but may jeopardize the child or may require intervention to prevent one of the other outcomes listed in the definition above.

### **4.2 Analysis Approaches**

#### **4.2.1. Baseline Characteristics**

Baseline characteristics will be summarized using data obtained at EIT Study entry (and subsequently entered into the Tatelo Study database), as well as data collected at Tatelo Study entry on the demographics form (primarily SES information, which may have changed from the prior EIT Study collection), and also age at Tatelo entry. Data from EIT will include: maternal ART regimen at delivery; birth weight and gestational age; baseline plasma HIV RNA and PBMC DNA prior to ART start; age at EIT entry; whether the child ever rebounded after 24 weeks on ART (and length of prior virologic rebound on ART if any).

#### **4.2.2. Primary outcomes**

1. AEs will be summarized generally (any graded event) and specifically (any SAE, defined above, or any AE determined by the study team to be related to one or both bNAb

infusion). Summaries will include listings by child of all graded events and summaries by frequency of AEs by event (including all graded events and focusing on SAEs and bNAb-related AEs).

2. Cumulative proportion of children experiencing SAEs during follow-up (until 30 days after last study visit for each participant) and proportion of potentially bNAb-related events. In particular, proportions of children experiencing the following events will be summarized along with 95% exact confidence intervals (based on the Clopper-Pearson method). The denominators for the following are all participants who received at least one infusion of a bNAb in Step 1.
  - a. At least one graded AE (of any grade)
  - b. At least one grade 3 or higher AE
  - c. At least one SAE (as defined above)
  - d. At least one potentially bNAb-related AE of any grade
  - e. At least one potentially bNAb-related AE grade 3 or higher
  - f. At least one potentially bNAb-related SAE
3. Proportion of children, among those receiving at least one infusion of a bNAb in Step 1, who maintain HIV-1 RNA in plasma less than 400 copies/mL at least 32 weeks after initiating dual bNAb treatment (i.e., 24 weeks after withdrawal of standard ART, which is through week 24 of Step 2) will be calculated along with a 95% confidence interval (based on exact Clopper-Pearson confidence limits).
4. Repeat #3 but considering only those children who enter Step 2 and discontinue ART.
5. Repeat #3 and #4 but considering the maintenance of less than 40 copies/mL (rather than 400 copies/mL).
6. Time from Step 2, Day 0 to HIV-1 RNA  $\geq$  400 copies/mL will be analyzed using Kaplan-Meier methods, with censoring at last available HIV-1 RNA measurement in Step 2 if lost to follow-up or administratively at Step 2, Week 24. This will be done among all participants receiving at least one infusion of a bNAb, and among those who entered Step 2 and discontinued ART.
7. Repeat #6 but considering time to HIV-1 RNA  $\geq$  40 copies/mL.
8. Time to re-suppression to  $<$  40 copies/mL (and  $<$  400 copies/mL) will be analyzed using Kaplan-Meier methods among those who entered Step 3 because of virologic failure in Step 2; time will be measured from the day of re-starting ART in Step 3 (Step 3 Day 0).

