1.9. Primary Endpoints and Analyses

Aim 1: The primary endpoints will be (1) the frequency and severity of treatment-associated adverse events, and (2) the proportion of children who maintain HIV-1 plasma RNA <400 copies/mL (and <40 copies/mL), after initiating VRC01LS and 10-1074 infusions (24 weeks after withdrawal of standard ART). Secondary endpoints will include pharmacokinetic profiles of all children who receive VRC01LS and 10-1074 and growth characteristics (height and weight z-scores) of virally suppressed children receiving bNAbs.

Aim 2: Viral reservoirs during treatment with VRC01LS and 10-1074 will be evaluated in blood samples (PBMCs) using a novel single-template, near full-length viral sequencing assay that provides information on the complete spectrum of HIV-1 DNA copies integrated into host chromosomes. This approach will allow us to evaluate defective vs. intact HIV-1 genomes, antiretroviral drug and cytotoxic T-lymphocyte (CTL) escape variants and longitudinal viral sequence evolution in total CD4 T cells as well as in phenotypically-complex subsets of CD4 T cells known to be critical for viral reservoir stabilization. Cell-associated HIV-1 RNA and plasma RNA will be simultaneously analyzed and sequenced. If rebound occurs during analytic treatment interruption (ATI), viral reservoir parameters will be correlated to viral rebound kinetics, to pharmacokinetic measurements of bNAbs, and to antiviral immune parameters determined in Specific Aim 3.

Aim 3: We will use comprehensive phenotypic and functional assays to profile effects of VRC01LS and 10-1074 treatment on biomarkers of immune activation and on innate cellular immune responses, coupled with RNA-Seq-based gene expression studies in selected immune cell subsets. In addition, the evolution of neutralizing antibody breadth and the frequency and functionality of HIV-1-specific T cells will be analyzed, and combined with viral sequencing data (generated in specific aim 2) to identify viral immune escape.

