8.2. Adverse Event Reporting

All adverse events (Grade 1 or higher), including all infusion reactions, will be recorded on an Adverse Event Log. Potential infusion reactions will also be described on the Infusion Reaction form.

8.2.1. Expedited Adverse Event Reporting to DAIDS: Requirements, definitions and methods for expedited reporting of AEs are outlined in Version 2.0 of the DAIDS EAE Manual, which is available on the RSC website at <https://rsc.niaid.nih.gov/clinical-research-sites/manual-expedited-reporting-adverse-events-daims>.

The DAIDS Adverse Experience Reporting System (DAERS), an internet-based reporting system, must be used for expedited AE reporting to DAIDS. In the event of system outages or technical difficulties, expedited AEs may be submitted via the DAIDS EAE Form. For questions about DAERS, please contact **NIAID CRMS Support** at [contact]. Site queries may also be sent from within the DAERS application itself.

Where DAERS has not been implemented, sites will submit expedited AEs by documenting the information on the current DAIDS EAE Form. This form is available on the RSC website: <https://rsc.niaid.nih.gov/clinical-research-sites/paper-eae-reporting>. For questions about expedited reporting, please contact DAIDS RSC ([contact]).

8.2.2. Reporting Requirements for this Study: The SAE Reporting Category, as defined in Version 2.0 of the DAIDS EAE Manual, will be used for this study.

VRC01LS and 10-1074 are the only study agents for which *expedited* reporting is required for SAEs. The Suspected Unexpected Serious Adverse Reactions (SUSAR) reporting category will be used in all other circumstances, until 30 days after study completion for each participant.

In addition to all SAEs meeting the above criteria, all grade 3 or higher serum sickness, grade 3 or higher urticarial or other hypersensitivity reactions, and grade 4 injection site reactions must also be reported as EAEs in this study.

8.2.3. Grading Severity of Events: The most current Division of AIDS Table for Grading the Severity of Adult and Pediatric Adverse Events (DAIDS AE Grading Table) at the time that the study opens will be used, and is available on the RSC website at <https://rsc.niaid.nih.gov/clinical-research-sites/daids-adverse-event-grading-tables>.

8.2.4. Expedited AE Reporting Period: The *expedited* AE reporting period for this study is for 30 days following the final dose of VRC01LS and 10-1074.

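### SAP 4.2.2 items 2a–2c pool time on and after bNAbs despite unequal on-bNAb time, and SAP 1.1 can close the analysis before the 30-day safety window ends

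*SAP*

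**What the plan says.** - **Outcome and window.** SAP 3.1 makes graded AEs a primary outcome, "measured through 30 days after last study visit". SAP 4.2.2 item 2 repeats that end point: "Cumulative proportion of children experiencing SAEs during follow-up (until 30 days after last study visit for each participant". The SAP version history says the window was clarified in version 2 to match the registered outcome.
- **Denominator and items.** Every proportion is taken over "all participants who received at least one infusion of a bNAb in Step 1", with Clopper-Pearson limits. Items a–c count any graded AE, any grade 3 or higher AE, and any SAE, whatever the cause. Items d–f repeat these for events judged possibly related, for example "At least one potentially bNAb-related AE grade 3 or higher". No split by Step, on-bNAb window or person-time is given.
- **Endpoint.** Protocol 1.9 names "the frequency and severity of treatment-associated adverse events".
- **Undosed time.** Of Step 3, SAP 4.1.3 says: "There were no bNAbs administered or PK draws done in Step 3". The SAE definition in SAP 4.1.7 requires only that the event follow a bNAb infusion and sets no time limit, so Step 3 events count.
- **Finalisation.** SAP 1.1: "Analyses will be finalized once the last participant has completed the Week 24 study visit of Step 3", once relevant queries are also resolved. It does not mention the 30 days.
- **Expedited reporting.** Protocol 8.2.4 states, for expedited reports only, that the "AE reporting period for this study is for 30 days following the final dose of VRC01LS and 10-1074".

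**The concern.** A simple proportion with at least one event grows with time observed. Here the time observed, and how much of it is on bNAbs, depends on when a child enrolled and whether the virus rebounded. The first six were planned for 32 weeks of Step 1 and later children for 8. Step 2 lasts up to 24 weeks and ends early on rebound. Every child is then scheduled for 24 weeks of Step 3 without bNAbs, and protocol 7.7.1 has signs and symptoms of any grade assessed at all visits, so those events are collected and enter the same numerators.

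In an uncontrolled trial of young children, a reader of items 2a–2c cannot tell how much of a reported proportion arose while bNAbs were being given. The SAP treats other outcomes with more care. SAP 4.2.3 reports growth changes separately for the bNAb-plus-ART and bNAb-alone periods, and SAP 4.3 lists duration of dual bNAb treatment as a possible risk factor for rebound.

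Separately, a primary safety outcome should not be finalised before its own window has run.

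**Working it through.** **Inputs.** Step 1: 8 weeks (later children) or 32 weeks (first six), SAP 4.1.3 and 4.3. Step 2: up to 24 weeks, with infusions every 4 weeks including Week 24 for completers but not at a rebound visit, protocol 7.7.1. Step 3: 24 weeks. 30 days = 30/7 = 4.3 weeks.

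**The plan's own figure.** Protocol 7.8 gives a minimum follow-up of 56 weeks. 8 + 24 + 24 = 56, so it reproduces for a later-enrolled child who completes Step 2.

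**Windows.** SAP window = last visit + 4.3. On-bNAb window = last infusion + 4.3. Weeks run from Step 1 Day 0. ART is taken as restarted at the exit visit.

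| Path | Last visit | SAP window | Last infusion | On-bNAb window | Difference | Share of SAP window |
|---|---|---|---|---|---|---|
| First-six completer | 32+24+24 = 80 | 84.3 | 56 | 60.3 | 24 | 28% |
| Later completer | 8+24+24 = 56 | 60.3 | 32 | 36.3 | 24 | 40% |
| Later child, rebound at Step 2 Week 2 | 8+2+24 = 34 | 38.3 | 8 | 12.3 | 26 | 68% |
| Later child leaving Step 1 at Week 5 | 5+24 = 29 | 33.3 | 4 | 8.3 | 25 | 75% |

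Among the children shown who enter Step 2, the on-bNAb window runs from 12.3 to 60.3 weeks, a ratio of 60.3/12.3 = 4.9, yet each child counts once. The first-six row assumes no Covid-19 infusion pause. Letter of Amendment 3 allowed one, of unstated length.

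**Effect on a proportion.** The documents give no background event rate, so a constant rate r per child-year, unrelated to bNAbs, is assumed. P(at least one event) = 1 − exp(−r × weeks/52.18). For a later completer:

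| Assumed r | On-bNAb window (36.3 weeks) | SAP window (60.3 weeks) |
|---|---|---|
| 0.05 | 3.4% | 5.6% |
| 0.1 | 6.7% | 10.9% |
| 0.2 | 13.0% | 20.6% |
| 0.5 | 29.4% | 43.9% |
| 1 | 50.1% | 68.5% |
| 2 | 75.1% | 90.1% |
| 5 | 96.9% | 99.7% |

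The gap is 2.2 points at r = 0.05, 18.4 at r = 1 and 2.8 at r = 5. It is large only for middling rates.

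**The last 30 days.** Only children whose last visit falls within 30 days of finalisation lose time. Protocol 5.5 caps enrolment at two per week. If children enrolled at that cap, followed equal paths and queries closed at once, the missing days would be 2 × (30 + 23 + 16 + 9 + 2) = 160, or 160/365 = 0.44 child-years. At assumed rates of 0.5, 1 and 2 per year that is 0.22, 0.44 and 0.88 events. Unequal paths could bring last visits closer together.

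**Residual exposure.** Protocol 2.1.8.2 plans on a 24-day half-life for 10-1074. Thirty days is 30/24 = 1.25 half-lives, leaving 2^−1.25 = 42%. Step 3 spans 168/24 = 7 half-lives. Protocol 2.1.8.1.1 calls the VRC01LS half-life very long and gives no figure.

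**The case against.** The SAP follows protocol 10.1.1, which asks for a cumulative proportion over follow-up. The window was set deliberately to match the registered outcome, and SAP 4.1.4 calls the analyses descriptive. Detailed tables are left to an Analysis Implementation Plan that is not among the documents, so a by-Step table may exist there. Long follow-up is sensible for antibodies that persist. Rates by Step also have a bias of their own. Step 2 has 15 scheduled visits in 24 weeks, while Step 3 has three after ART restarts, with haematology only at Weeks 4 and 24 and liver tests only at Week 4. Equal underlying risk would tend to look worse in Step 2.

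Most of this stands. It is why the all-follow-up proportions should stay and why rates by Step can only be descriptive. It does not remove the gap: the period over which a primary safety outcome is read belongs in the SAP.

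Several stronger inferences are tempting but unsupported:
- *Step 3 follow-up is unequal by design.* It is scheduled at 24 weeks for all. The designed inequality lies in bNAb time.
- *The window hangs on any contact.* The anchor is the last study visit.
- *The plan does not measure bNAb safety.* Items 2d–2f are restricted to possibly related events, item 1 lists every graded event by child, and SAP section 5 reports infusion reactions.
- *Protocol 8.2.4 already sets an on-treatment analysis window.* It governs expedited reporting only, so it is a precedent and not a rule.
- *All 20 children lose their last 30 days* (20 × 30/365 = 1.6 events at one per year). Earlier finishers' windows have closed by then. Protocol 8.2.2 also keeps reporting of suspected unexpected serious reactions open to 30 days after study completion, although no visit is scheduled then.
- *Early rebounders will look safer.* No planned analysis compares AEs by rebound status, and rebounders have extra weekly Step 3 visits.

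**Conclusion.** The concern holds for items 2a–2c and for the finalisation trigger, and is worth fixing. On the paths shown, between 28% and 75% of a child's AE window lies more than 30 days after the last infusion. For a later completer, that could raise an all-cause proportion by about 2 to 18 points with no bNAb effect, over assumed background rates of 0.05 to 5 per child-year. Sampling error at 20 children is larger: the protocol's own example of 70% has exact limits of 46% to 88%. The problem is therefore one of interpretation and not a miscalculation. Items 2d–2f partly answer it, but relatedness is decided by site staff and the study team, who know the treatment and have no control group to compare with.

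The truncation is small, under one expected event in the illustration, but it falls in a primary outcome and no collection method is stated. The window calculations assume the scheduled Step lengths and no infusion pause.

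**What to change.** 1. In SAP 4.2.2 item 2, keep the all-follow-up proportions as they are.
2. Beside them, report items a–f from the first Step 1 infusion to 30 days after the last infusion.
3. Add event counts, person-time and events per child-year with exact Poisson limits for Steps 1, 2 and 3.
4. State that Step 3 carries residual bNAb exposure and has fewer visits and laboratory tests, so the rates by Step are descriptive and not a clean off-drug contrast.
5. In SAP 1.1, set the finalisation trigger at no less than 30 days after the last participant's last study visit, and say how events in those 30 days are collected.

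The cost is a few table columns and up to 30 days' delay. The limits are wide intervals from little person-time per Step, and confounding of the by-Step rates with visit intensity.
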